Appendix 7: WHO Bleeding Scale

WHO Bleeding Scale[15]

Grade	WHO Bleeding Scale
0	No bleeding
1	Petechial bleeding
2	Mild blood loss (clinically significant)
3	Gross blood loss, requiring transfusion (severe)
4	Debilitating blood loss, retinal or cerebral, associated with fatality

[figure not shown]

1. INTRODUCTION

This “Statistical Analysis Plan (SAP)” presents details, including technical matters, of the efficacy and safety analyses described in Section “[8. STATISTICAL ANALYSIS](#)” of the protocol 1423M0634 for the clinical trial entitled “A Phase 3 Randomised, Double-blind, Placebo-controlled Study to Assess the Safety and Efficacy of S-888711 (Lusutrombopag) for the Treatment of Thrombocytopenia in Patients with Chronic Liver Disease (CLD) Undergoing Elective Invasive Procedures (L-PLUS2)”. Details of output (or mock-ups of tables, listings and figures) from analyses in this SAP, will be included in the document prepared separately. Details of the analyses of pharmacokinetics (PK) and pharmacokinetics/pharmacodynamics will also be described in a separate document.

All the analyses described in this SAP will be performed in the Biostatistics Dept., Shionogi & Co., Ltd.

2. STUDY OVERVIEW

This is a phase 3, multinational, randomized, double-blind, placebo-controlled study to assess the safety and efficacy of S-888711 for the treatment of thrombocytopenia in patients with CLD undergoing elective invasive procedures. The study consists of 3 periods:

[figure not shown]
- Screening period: up to 28 days prior to randomization
- Treatment period: up to 7 days (Days 1 to 7)
- Post-treatment period: through 28 days post-treatment

The maximum study duration for each patient will be 63 days. Potential patients who provide written informed consent will be screened for eligibility, and eligible patients will be randomized in a 1:1 ratio to either S-888711 3 mg once daily for up to 7 days or matched placebo control. The randomization will be stratified by primary invasive procedure (liver ablation/coagulation or other invasive procedures) and baseline platelet count ($< 35 \times 10^9/L$ or $\geq 35 \times 10^9/L$).

Patients will begin once daily treatment with assigned study medication on Day 1 after randomization and will receive study medication for up to 7 days. A platelet count will be performed on Days 5, 6, and 7 prior to administration of study medication. After the final dose of study medication, patients will continue the protocol-specified assessments and procedures in the Post-treatment period.

The planned invasive procedure will be performed in the Post-treatment period between Days 9 and 14. A platelet count will be performed on or after Day 8, but no more than 2 days prior to the elective invasive procedure in order to assess the need for a platelet transfusion before the planned elective procedure. A preoperative platelet transfusion must be performed if the platelet count is $< 50 \times 10^9/L$.

Study Schematic

3. STUDY OBJECTIVES

3.1 Primary Objective

The primary objective of this study is to compare the efficacy of S-888711 with placebo for the treatment of thrombocytopenia in patients with CLD who are undergoing elective invasive procedures.

3.2 Secondary Objective(s)

The secondary objectives of the study are:

- To assess the safety and tolerability of S-888711 treatment compared with placebo.
- To assess the platelet response following treatment with S-888711 compared with placebo.
- To assess the pharmacodynamics (PD) and PK of S-888711.

4. STUDY DESIGN

4.1 Schedule of Assessments

Schedule of assessments is shown in [Appendix 1](#).

4.2 Study Blinding and Randomization

The study will be conducted in a double-blind manner using a placebo matching the active drug in appearance, labelling and packaging. An IVRS/IWRS will be used for central patient randomization and study drug assignment. IVRS/IWRS will assign drug identifiers according to a randomization schedule. Only an unblinded Contract Research Organization (CRO) or designee will have the authority to assign the drug identifiers. All patients, the investigator, all study personnel, and data analysts will be blinded to the

treatment assigned at randomization until database lock. The randomization schedule will be kept confidential and will not be accessible to anyone until unblinding, except for Drug Supply Management staff, IVRS/IWRS Clinical Coordinator(s), IVRS/IWRS vendor staff, unblinded statistician on the Independent Safety Committee, and for reporting suspected unexpected serious adverse reaction (SUSAR) as required by local regulation.

Eligible patients will be randomized to one of the two treatment groups (S-888711 3 mg/day for up to 7 days, or placebo for up to 7 days) in a ratio of 1:1. Randomization will be stratified by the primary invasive procedure and the platelet count at baseline as follows:

- Primary invasive procedure: liver ablation/coagulation or other invasive procedures
- Platelet count at baseline: $< 35 \times 10^9/\text{L}$ or $\geq 35 \times 10^9/\text{L}$

4.3 Determination of Sample Size

Two hundred patients with CLD and thrombocytopenia who are scheduled to undergo elective invasive procedures will be randomized into either of two treatment groups (100 patients per group).

In the phase 3 study (Study 1304M0631) conducted in Japan, the proportion of patients who required no platelet transfusion prior to the primary invasive procedure was 79.2% in the S-888711 3 mg group and 12.5% in the placebo group. The difference in the proportion of patients was 66.7% and its 95% confidence interval (CI) was [51.9%, 81.5%]. Based on the results, it was assumed that the difference in the primary endpoint to be obtained in this study is 50% between S-888711 and placebo groups. Assuming that the proportion of patients who meet the primary endpoint is 20% in the placebo group and 70% in the S-888711 treatment group, 100 patients per arm will provide 99% power to detect a difference of 50% between S-888711 and placebo groups at a two-sided significance level of 0.05.

With 100 patients per arm, from the safety point of view, the sample size will assure at least 95% probability to detect an adverse event (AE) with an incidence of 3% or more.

5. ANALYSIS POPULATIONS

5.1 Intention-to-Treat (ITT) Population

Intention-to-Treat (ITT) Population will include all randomized patients. Patients will be analyzed according to the treatment to which they were randomized. This population is the primary population for the analysis of efficacy.

5.2 Per Protocol (PP) Population

Per Protocol (PP) Population will include all randomized patients who have no major protocol deviations pertaining to the efficacy evaluation. These deviations will be

determined prior to unblinding of the study data. This population will be used in a sensitivity analysis of the primary endpoint.

5.3 Safety Analysis Population

Safety Analysis Population will include all randomized patients who actually receive at least 1 dose of the study drug. Patients will be analyzed by the treatment they actually received, rather than by the designated treatment to which they were randomized. If patients received both S-888711 and placebo, they will be considered as the S-888711 group. This population is the primary population for the analysis of safety.

6. OVERALL CONSIDERATIONS FOR DATA ANALYSES AND HANDLING

6.1 Statistical Reporting

In principle, summary statistics, including the number of patients, arithmetic mean, standard deviation (SD), median, and minimum and maximum values, will be calculated for continuous variables. The number and proportion of patients in each category will be calculated for categorical variables.

In general, all tabulations will be presented by treatment group. Individual patient data and any derived data will be summarized by treatment group and listed by patient. All the analyses and listings will be performed using SAS Version 9.2 or higher.

6.2 Statistical Testing

Unless otherwise noted, all statistical tests will be performed at a two-sided significance level of 0.05.

A gatekeeping procedure will be employed for sequentially testing the important secondary endpoints (see [Appendix 2](#)). If the primary endpoint is statistically significant, the secondary endpoints will be tested at the 0.05 level (two-sided) in sequence.

Sequential testing for the secondary endpoints will be conducted in the following order:

- The comparison between S-888711 and placebo in the proportion of patients who require no platelet transfusion during the study
- The comparison between S-888711 and placebo in the proportion of responders: patients who achieve a platelet count of $\geq 50 \times 10^9/\text{L}$, with an increase of $\geq 20 \times 10^9/\text{L}$ from baseline at any time during the study
- The comparison between S-888711 and placebo in the duration of platelet count $\geq 50 \times 10^9/\text{L}$
- The comparison between S-888711 without platelet transfusion and placebo with platelet transfusion in the duration of platelet count $\geq 50 \times 10^9/\text{L}$

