3. INVESTIGATIONAL PLAN

3.1 Overall Study Design and Plan

This is a phase 3, multinational, randomised, double-blind, placebo-controlled study to assess the safety and efficacy of S-888711 for the treatment of thrombocytopenia in patients with CLD undergoing elective invasive procedures. A schematic of the study design is provided in [Figure 2-1](#).

The study consists of 3 periods:

- Screening period: up to 28 days prior to randomisation
- Treatment period: 7 days (Days 1 to 7)
- Post-treatment period: through 28 days post-treatment

The maximum study duration for each patient will be 63 days. Potential patients who provide written informed consent will be screened for eligibility, and eligible patients will be randomised in a 1:1 ratio to either S-888711 3 mg once daily for up to 7 days or

matched placebo control. The randomisation will be stratified by primary invasive procedure (liver ablation/coagulation or other invasive procedures) and baseline platelet count ($< 35 \times 10^9/\text{L}$ or $\geq 35 \times 10^9/\text{L}$).

Patients will begin once daily treatment with assigned study medication on Day 1 after randomisation and will receive study medication for up to 7 days. A platelet count will be performed on Days 5, 6, and 7 prior to administration of study medication. After the final dose of study medication, patients will continue the protocol-specified assessments and procedures in the Post-treatment period.

[figure not shown]
The planned invasive procedure will be performed in the Post-treatment period between Days 9 and 14. A platelet count will be performed on or after Day 8, but no more than 2 days prior to the elective invasive procedure in order to assess the need for a platelet transfusion before the planned elective procedure. A pre-operative platelet transfusion must be performed if the platelet count is $< 50 \times 10^9/\text{L}$. Patients may be admitted to the study centre for the elective invasive procedure if required.

The need for the invasive procedure will be reassessed in the event of any of the following:

- Platelet count $\geq 200 \times 10^9/\text{L}$
- Administration of an antithrombotic drug
- In the opinion of the investigator, the procedure is no longer in the patient's best interest because of an AE or other concern
- The patient requests cancellation of the elective procedure after randomisation

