8.2 Rationale for Target Sample Size and Stratification Factors

Two hundred patients with CLD and thrombocytopenia who are scheduled to undergo elective invasive procedures will be randomised into either of two treatment groups (100 patients per group).

In the phase 3 study (Study 1304M0631) conducted in Japan, the proportion of patients who required no platelet transfusion prior to the primary invasive procedure was 79.2% in S-888711 3 mg group for up to 7 days and 12.5% in the placebo group. The difference of proportion of patients was 66.7% and its 95% confidence interval (CI) was [51.9%, 81.5%]. Based on the results, it was assumed that the difference in the primary endpoint to be obtained in this study is 50% between S-888711 and placebo groups. Assuming that the proportion of patients who meet the primary endpoint is 20% in the placebo group and 70% in the S-888711 group, 100 patients per arm will provide 99% power to detect a difference of 50% between S-888711 and placebo groups at a two-sided significance level of 0.05.

With 100 patients per arm, from the safety point of view, the sample size will assure at least 95% probability to detect an AE with an incidence of 3% or more.

Since the risk of bleeding is different for each elective procedure, primary invasive procedure has been selected as a stratification factor as per the phase 3 Japanese study (Study 1304M0631). Furthermore, in the Japanese study, the proportion of patients in the 3 mg group who received no platelet transfusion prior to the primary invasive procedure was relatively low in the group whose platelet count at baseline was $< 35 \times 10^9/L$ (57.1%, 4/7 patients) compared to the group whose platelet count at baseline was $\geq 35 \times 10^9/L$

(82.9%, 34/41 patients). Thus, for the current study, platelet count at baseline has been selected as an additional stratification factor

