8.10.1.2 Secondary Endpoint Analysis

A gatekeeping strategy will be employed for sequentially testing the important secondary hypotheses. If the primary hypothesis is statistically significant, the secondary hypotheses will be tested in sequence at a level of 0.05 (two-sided). Sequential testing for the secondary endpoints will be conducted in the following order:

- The comparison between S-888711 and placebo on the proportion of patients who require no platelet transfusion during the study
- The comparison between S-888711 and placebo on the proportion of responders: patients who achieve a platelet count of $\geq 50 \times 10^9/\text{L}$, with an increase of $\geq 20 \times 10^9/\text{L}$ from baseline at any time during the study
- The comparison between S-888711 and placebo for the duration of platelet count $\geq 50 \times 10^9/\text{L}$

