8.10.1.2.3 Duration of the Increase in Platelet Count

Median and quartiles for the duration of increased platelet count will be calculated in each treatment group with or without platelet transfusions. The duration will be compared between the S-888711 group and placebo group using Wilcoxon rank sum test.

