9.2.3.1 Analysis

Median and quartiles for the duration of the increase in platelet count will be calculated by treatment group with or without platelet transfusions. The duration in the S-888711 group will be compared with that in the placebo group using van Elteren test stratified with platelet transfusion during the study. In addition, to explore an efficacy of S-888711 compared to platelet transfusion, the duration in the S-888711 group without platelet transfusion will be compared with that in the placebo group with platelet transfusion using Wilcoxon rank sum test.

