13. CHANGES FROM PROTOCOL

- An analysis using the van Elteren is added in order to compare the duration of the increase in platelet count between S-888711 and placebo group for the ITT population (see [Section 9.2.3](#))
- Summary of significant TEAEs is removed because this event was not defined in the protocol.

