Appendix 2 Testing Procedure for Primary and Important Secondary Endpoints

S-888711 for up to 7 days vs. Placebo

Testing the Primary Efficacy Endpoint:

The null hypothesis is that there is no difference between S-888711 for up to 7 days and placebo groups regarding the proportion of patients, who require no platelet transfusion prior to the primary invasive procedure and no rescue therapy for bleeding from randomization until 7 days after the primary elective procedure.

↓ if rejected^a

Testing the Secondary Efficacy Endpoint 1:

The null hypothesis is that there is no difference between S-888711 for up to 7 days and placebo groups regarding the proportion of patients who require no platelet transfusion during the study.

↓ if rejected^a

Testing the Secondary Efficacy Endpoint 2:

The null hypothesis is that there is no difference between S-888711 for up to 7 days and placebo groups regarding the proportion of patients who achieve a platelet count of $\geq 50 \times 10^9/L$ with an increase of $\geq 20 \times 10^9/L$ from baseline at any time during the study.

↓ if rejected^a

Testing the Secondary Efficacy Endpoint 3:

The null hypothesis is that there is no difference between S-888711 and placebo groups regarding the duration of the platelet count $\geq 50 \times 10^9/L$.

↓ if rejected^a

Testing the Secondary Efficacy Endpoint 4:

The null hypothesis is that there is no difference between S-888711 for up to 7 days without platelet transfusion and placebo with platelet transfusion groups regarding the duration of the platelet count $\geq 50 \times 10^9/L$.

[a] If superiority of S-888711 to placebo is demonstrated at the two-sided significance level of 0.05, then the next hypothesis will be tested.

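### The fourth gatekept test compares untransfused S-888711 patients with transfused placebo patients, groups formed after randomisation, and cannot support a confirmatory claim

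*SAP*

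**What the plan says.** SAP 6.2 lists four secondary tests, each at two-sided 0.05 and each opened by success on the one before. The fourth is "The comparison between S-888711 without platelet transfusion and placebo with platelet transfusion in the duration of platelet count" at or above 50 × 10⁹/L. SAP Appendix 2 repeats it as the last hypothesis in its chain, worded as follows: "The null hypothesis is that there is no difference between S-888711 for up to 7 days without platelet transfusion and placebo with platelet transfusion groups" on that duration.

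SAP 9.2.3.1 gives the same analysis a different status: "to explore an efficacy of S-888711 compared to platelet transfusion, the duration in the S-888711 group without platelet transfusion will be compared" with transfused placebo patients, by an unstratified Wilcoxon rank sum test.

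Protocol 8.10.1.2 and the synopsis have three secondary tests, all between the randomised arms. The last is "The comparison between S-888711 and placebo for the duration of platelet count" at or above 50. For that endpoint, protocol 8.10.1.2.3 states: "The duration will be compared between the S-888711 group and placebo group using Wilcoxon rank sum test". It uses the split by transfusion for medians and quartiles. SAP 13 records one change to this analysis, "An analysis using the van Elteren is added in order to compare the duration of the increase in platelet count", and does not mention the fourth test.

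Protocol 3.1 sets the rule that largely creates the groups: "A pre-operative platelet transfusion must be performed if the platelet count is" under 50 × 10⁹/L. SAP 9.2.3 defines duration as days at or above 50, interpolated between scheduled counts, and counts taken after a transfusion are not excluded.

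**The concern.** The comparison looks like drug against transfusion, but neither side is a randomised group. It drops S-888711 patients who were transfused and placebo patients who were not. In broad terms these are the weaker responders on one arm and the better-placed patients on the other. Because the sorting rule and the outcome share the 50 × 10⁹/L threshold, a difference in duration is partly built in.

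Sorting is not by count alone. Rescue transfusion is allowed whatever the count (protocol 6.2.1.3), and a patient who has no procedure may go untransfused. Post-transfusion counts also add to placebo duration, so the bias can shrink or even reverse. The Wilcoxon test adjusts for none of this, not even for the baseline-count stratum used at randomisation.

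At stake is the status of the result. If the drug works and the earlier gates open, a significant fourth test would carry confirmatory weight for S-888711 against platelet transfusion while mixing drug effect with patient selection. An analysis also cannot be exploratory in one section and alpha-controlled in another.

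**Working it through.** **1. The plan's own figure.** The SAP gives no power or effect size for the fourth test. Its primary planning figure (SAP 4.3) is 70% against 20%, 100 per arm, 99% power. The pooled rate is 0.45, so the null standard error is √(2 × 0.45 × 0.55/100) = 0.0704. The alternative standard error is √((0.7 × 0.3 + 0.2 × 0.8)/100) = 0.0608. Power = Φ((0.5 − 1.96 × 0.0704)/0.0608) = Φ(5.95), above 0.9999. The stated 99% is a safe floor, so at these rates the first gate would almost surely open.

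**2. Who is compared.** Treat primary-endpoint failure as transfusion (an assumption). About 70 untransfused S-888711 patients then meet about 80 transfused placebo patients, and 30 + 20 = 50 of 200 (25%) are left out. Assume also that S-888711 never causes a transfusion. Per 100 patients, 20 are transfused on neither treatment, 50 on placebo only and 30 on both.
- Untransfused on S-888711: 20 + 50 = 70, of whom 20/70 = 29% would also be untransfused on placebo.
- Transfused on placebo: 50 + 30 = 80, of whom 30/80 = 37.5% would also be transfused on S-888711.

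These two fractions have no matching patient type on the other side.

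**3. Baseline count.** Protocol 8.2 says the untransfused proportion in the Japanese 3 mg arm "was relatively low in the group whose platelet count at baseline was" below 35 × 10⁹/L: 4/7, against 34/41 at 35 or more. Turned round, baseline was 35 or more in 34/38 (89%) of patients without transfusion and in 7/10 (70%) of the rest. Fisher's exact p is 0.15, so this is suggestive only.

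**4. The test alone, with equal durations in both arms.** Model: a latent prognosis has correlation ρ with duration, the best 70% of S-888711 patients and the worst 80% of placebo patients are kept, and 4,000 trials are run per value. The documents give no ρ.

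| ρ | Rejection at two-sided 0.05 |
|---|---|
| 0 | 0.05 |
| 0.2 | 0.17 |
| 0.3 | 0.33 |
| 0.5 | 0.74 |
| 0.7 | 0.98 |

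From ρ = 0.3 upward every rejection favoured S-888711. The whole-arm comparison on the same data stayed between 0.044 and 0.053.

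**5. Platelet trajectories with the gates.** From the documents: 100 per arm, baseline under 50, the SAP visit days and duration formula, procedure on Days 9 to 14, count no more than 2 days before, transfusion if below 50, and placebo untransfused rates of 12.5% or 20%. Assumed: between/within-patient SD of 7/3, 5/5 or 3/7, transfusion lift of 0 to 40 × 10⁹/L decaying over 2, 4 or 7 days, and 5% with no procedure. Rescue was ignored, and an unstratified Wald test stood in for CMH.
- *Inert drug, test run alone* (78 scenarios × 600 trials): rejection was 8% to 100%. It exceeded 50% in favour of S-888711 in 43 scenarios and in favour of transfused placebo in 3.
- *Inert drug, earlier gates applied:* the fourth test was reached and rejected in 0 of 78 × 600 = 46,800 trials.
- *Working drug, 70% against 20%* (126 scenarios × 200 trials): the benchmark is the mean difference among patients transfused on placebo but not on S-888711. The contrast exceeded it in all 126, by 0.5 to 5.5 days, and by 0.5 to 3.9 days in the 87 scenarios where the gates opened in over half of trials. In one scenario a true 0.8 days appeared as 2.1 days with the gates open in 96% of trials. The true difference was positive throughout (0.7 to 16 days).

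**The case against.** The strongest reply is that no false claim has been shown. The gates stop an inert drug, the high rejection rates in step 4 and for the inert drug describe a test run without its gates, and with a working drug the direction in the 126 scenarios was right. The Wilcoxon test is valid for the null as Appendix 2 words it, namely equal distributions in two selected subsets, and the SAP plans no effect estimate for this contrast that could be overstated. All of that stands. It does not help, because that null does not isolate drug against transfusion, which is the purpose SAP 9.2.3.1 states.

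The size depends on the inputs, and 0.8 appearing as 2.1 days is an unfavourable ratio. Protocol 1.3 reports 20 days or more at or above 50 for untransfused S-888711 patients in phase 2b. In one further set of 36 assumed scenarios, 20 reached about that duration. There the true difference was 8.8 to 23.8 days, the contrast was off by −0.1 to +3.0 days, and in two scenarios it was not above the truth. In another 36, the contrast was too high in every scenario, by 0.6 to 5.7 days (0.6 to 4.9 where untransfused duration was 20 days or more), and in a few a true difference at or below zero appeared positive. The bias is usually upward, and its size is uncertain.

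Other points stand as limits. The 29% and 37.5% are illustrations, since primary failure also covers rescue therapy, withdrawal and no procedure. The baseline evidence is small and comes from treated patients only. The transfusion-split Wilcoxon may be a reading of protocol 8.10.1.2.3 rather than a late addition, but it is still not in the protocol's sequence and not declared in SAP 13.

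**Conclusion.** The concern holds. The fourth test sits in the confirmatory sequence in SAP 6.2 and Appendix 2, is exploratory in SAP 9.2.3.1, is absent from protocol 8.10.1.2 and is undeclared in SAP 13. Its groups form after randomisation, largely by the threshold that defines the outcome. That conclusion needs no simulation.

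The simulations only indicate size. With a working drug the overstatement was mostly between about half a day and five and a half days, under assumed SDs, transfusion lifts and effect shapes that the documents do not give. Familywise error under the complete null is not inflated, and because the test comes last, the primary test and secondary tests 1 to 3 are unaffected. What fails is the claim that a significant fourth result would appear to support. The point should be fixed, but it does not threaten the trial's main conclusion.

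**What to change.** Delete the fourth bullet in SAP 6.2 and Secondary Efficacy Endpoint 4 in Appendix 2, so that the order of endpoints ends at the third, as in protocol 8.10.1.2. The move from Wilcoxon to van Elteren for that third endpoint is a separate change.

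Keep the comparison in SAP 9.2.3.1 as descriptive or explicitly exploratory. State that the groups are defined after randomisation, that it lies outside the alpha-controlled sequence, that any p-value is nominal, and that no superiority over platelet transfusion will be claimed from it. List it in SAP 13 as a change from the protocol.

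The cost is wording in four places. No data collection, sample size or alpha changes, and the primary test and secondary tests 1 to 3 keep their order and level. The sponsor gives up one supplementary confirmatory claim.
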